4.2 EXCLUSION CRITERIA

1. Children with past or present intracranial tumor growth as confirmed by an MRI scan (with contrast).
2. History of radiation therapy or chemotherapy.
3. Malnourished children defined as:
 - a. Serum albumin below the lower limit of normal (LLN) according to the reference ranges of central laboratory, AND
 - b. Serum iron below the lower limit of normal (LLN) according to the reference ranges of central laboratory, AND
 - c. BMI < -2 SD for age and sex.
4. Children with psychosocial dwarfism.

OPKO Biologics	Protocol for Clinical Study CP-4-004	Page 43 of 133
Effective Date: Date of final electronic approval		

5. Children born small for gestational age (SGA = birth weight and/or birth length < -2 SD for gestational age).
6. Presence of anti-hGH antibodies at screening.
7. Any clinically significant abnormality likely to affect growth or the ability to evaluate growth, such as, but not limited to, chronic diseases like renal insufficiency, spinal cord irradiation, etc.
8. Patients with diabetes mellitus.
9. Patients with impaired fasting sugar (based on WHO; fasting blood sugar >110 mg/dl or 6.1 mmol/l after repeated blood analysis).
10. Chromosomal abnormalities and medical “syndromes” (Turner’s syndrome, Laron syndrome, Noonan syndrome, Prader-Willi Syndrome, Russell-Silver Syndrome, SHOX mutations/deletions and skeletal dysplasias), with the exception of septo-optic dysplasia.
11. Closed epiphyses.
12. Concomitant administration of other treatments that may have an effect on growth such as anabolic steroids and methylphenidate for attention deficit hyperactivity disorder (ADHD), with the exception of hormone replacement therapies (thyroxin, hydrocortisone, desmopressin (DDAVP)).
13. Children requiring glucocorticoid therapy (e.g. asthma) that are taking a dose of greater than 400 µg/d of inhaled budesonide or equivalents¹ for longer than 1 month during a calendar year.
14. Major medical conditions and/or presence of contraindication to r-hGH treatment.
15. Known or suspected HIV-positive patient, or patient with advanced diseases such as AIDS or tuberculosis.
16. Drug, substance, or alcohol abuse.
17. Known hypersensitivity to the components of study medication.
18. Other causes of short stature such as coeliac disease, hypothyroidism and rickets.
19. The patient and/or the parent/legal guardian are likely to be non-compliant in respect to study conduct.
20. Participation in any other trial of an investigational agent within 30 days prior to Screening.

¹Approximately equivalent doses: Fluticasone: 264 µg/d; Beclomethasone: 504 µg/d; Flunisolide 1,000 µg/d; Triamcinolone: 1,000 µg/d.

OPKO Biologics	Protocol for Clinical Study CP-4-004	Page 44 of 133
Effective Date: Date of final electronic approval		

Specific exclusion criteria for Treatment Period V (LT-OLE-PEN):

21. Unresolved drug related SAE from previous treatment periods.
22. Diagnosis of cancer.
23. Patients who, based on the investigator's judgment, have a clinically significant or unstable medical or surgical condition that may preclude safe and complete study participation. Conditions may include cardiovascular, peripheral vascular, pulmonary, hepatic, renal, neurological and metabolic disease.
24. Concomitant administration of other treatments that may have an effect on growth such as anabolic steroids or replacement of sex hormones, with the exception of ADHD drugs or hormone replacement therapies (thyroxin, hydrocortisone, desmopressin [DDAVP]).
25. Unsatisfactory treatment response defined as improvement of height SDS of less than 0.2 SDS in a 6-month treatment interval if dose increase at this time point is not feasible.

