From the second year of the LT-OLE-PEN period and until marketing approval visits will be conducted every 3 months (months 3, 6, 9 and 12) ± 2 weeks, on day 4 (-1) post injection.

All visits assessments are detailed in section 5.4.2.

The investigator may conduct unscheduled visits, for safety reasons, or any other reason per investigator medical judgment.

Throughout the LT-OLE-PEN period, patients will continue to complete a patient diary at home to collect dosing and safety data.

Figure 1: Overall Study Design

* Patients from cohorts 1 and 2 who already started their second year of long term extension, will begin receiving 0.66 mg/kg/week as from their next scheduled visit

4. Study Population

In order to enroll up to 56 patients (allocated to 4 cohorts) into the Main Study, a sufficient number of pre-pubertal males aged 3 – 11 and females aged 3 – 10, with either isolated growth hormone deficiency (GHD) or GH insufficiency as a part of multiple pituitary hormone deficiency, will be recruited from 10 to 12 countries and 20 to 40 different centers. All centers will be specialized in the treatment and management of pediatric GHD.

The study population will consist of 2 subgroups:

1. Patients with peak GH level of [REDACTED] ng/ml (up to 40 patients).
2. Patients with peak GH level of [REDACTED] ng/ml and [REDACTED] ng/ml (up to 16 patients).

Patients must meet all of the inclusion and none of the exclusion criteria to be eligible. Patient eligibility will be verified by the study Medical Monitor before randomization.

OPKO Biologics	Protocol for Clinical Study CP-4-004	Page 41 of 133
Effective Date: Date of final electronic approval		

Patients who complete 12 months of treatment in the Main Study will be eligible to continue the treatment with MOD-4023 in a 12-month OLE period, and subsequent LT-OLE period and LT-OLE-PEN period until marketing approval in their country. The LT-OLE-PEN period will be extended on an annual basis until marketing approval in each country, subject to submission of an annual extension notification to the local EC/IRB.

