4.1 INCLUSION CRITERIA

1. Pre-pubertal child aged \geq 3 years old and not above 10 years for girls or 11 years for boys, with either isolated GHD, or GH insufficiency as part of multiple pituitary hormone deficiency.
2. Confirmed diagnosis of GHD by two different GH provocation tests defined as a peak plasma GH level of █ ng/ml¹, determined by central laboratory using a validated assay². If the patient has already been tested locally and reserve samples that were taken at appropriate time-points are available, these will be reanalyzed by the central laboratory³. Historical tests missing the -30 minutes time point will be accepted. If no reserve samples are kept (only for tests performed prior to site initiation), then the details of the locally performed tests will be reviewed by the Coordinating Investigator: if the results cannot be accepted, the patient will undergo both stimulation tests during the screening period and the samples will be analyzed by the central laboratory. At least one of the two stimulation tests (and preferably both) will be analyzed by the central laboratory. If the patient requires sex hormone priming (due to the age), and both stimulation tests must be performed during the Screening (no historical samples kept, or test was without priming), it is recommended to perform stimulation tests in consecutive setting in one day, or in two consecutive days, to avoid priming the patient twice. Local historical tests without sex-steroid priming will not be accepted for patients that require sex steroid priming according to the protocol.
3. Bone age (BA) must be not older than chronological age, and should be no greater than 9 years for girls and 10 years for boys.
4. Without prior exposure to any r-hGH therapy.
5. Impaired height and height velocity defined as:
 - a. Height (HT) of at least 2.0 standard deviations (SD) below the mean height for chronological age (CA) and gender according to the standards of Prader et al. (1989) (HT SDS \leq -2.0);
 - b. Annualized height velocity (HV) below the 25th percentile for CA (HV $<$ -0.7 SDS) and gender according to the standards of Prader et al. (1989). The interval

¹ Patients will be divided into two subgroups: Patients with peak serum GH levels after stimulation test █ ng/ml and patients with peak serum GH levels after stimulation test █ and █ ng/ml.

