4.6 REMOVAL, REPLACEMENT, OR EARLY WITHDRAWAL OF PATIENTS FROM THERAPY OR ASSESSMENT

Patients are free to discontinue their participation in the study at any time and without prejudice to further treatment. The Investigator must withdraw any patient from the study if that patient requests to be withdrawn, or if it is determined that continuing in the study would result in a significant safety risk to the patient.

Patients withdrawn from the study after starting treatment with MOD-4023 will not be replaced.

The patient's participation in this study may be discontinued due to the following reasons:

1. Request from regulatory agency, sponsor, primary care physician, or Investigator.
2. Patient (or parent/legal guardian) withdraws consent.
3. Adverse event (AE):
 - Occurrence of a malignancy during the course of study.
 - Evidence of growth of an intracranial tumor during the course of the study.
 - Development of benign intracranial hypertension, if the symptoms return following resumption of drug (after a temporary stop).
 - Occurrence of AE's following which the Investigator or the patient wishes to discontinue treatment (such as, but not limited to, slipped capital femoral epiphysis, scoliosis, avascular necrosis and development of lipoatrophy, etc.).
 - Development of a serious inter-current critical illness.
 - Abnormal laboratory values that affect the patient's safety (if discontinuation is considered necessary by the Investigator or the Sponsor Medical Monitor).

OPKO Biologics	Protocol for Clinical Study CP-4-004	Page 46 of 133
Effective Date: Date of final electronic approval		

4. A severe adverse drug reaction (if discontinuation of study medication is desired by the patient or considered necessary by the investigator or the Sponsor Medical Monitor). If the Investigator decision is made because of a SAE or clinically significant laboratory value, the Medical Monitor is to be alerted immediately.
5. Intake of prohibited concomitant medication.
6. Unsatisfactory treatment response defined as improvement of height SDS of less than 0.2 SDS in a 6-month treatment interval if dose increase at this time point is not feasible (Applicable for periods I-IV)
7. Patient is unwilling or unable to continue the study or is lost-to-follow-up.
8. Patient is non-compliant with study procedures/ study protocol.
9. Investigator decides that withdrawal from the study is in the best interest of the patient:

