 - Occurrence of neutralizing antibodies which, in the opinion of the Investigator, requires discontinuation of the patient.
 - Lack of patient compliance (if discontinuation is desired or considered necessary by the investigator or the Sponsor Medical Monitor).
 - A serious protocol deviation that affects the patient's safety or the accuracy and/or validity of data.
10. Patient meets one of the exclusion criteria during the study.
11. Any clinically significant change in the patient's medical condition.

Discontinuation rules specific to the LT-OLE-PEN period:

12. Positive urine pregnancy test or confirmed pregnancy. In case of confirmed pregnancy, the study drug should be discontinued and the Medical Monitor be alerted immediately.
13. When the patient reaches a growth rate of [REDACTED] 12 months (the interval between two height measurements should be at least 6 months).

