5.4 LONG-TERM OPEN LABEL EXTENSION PEN (LT-OLE-PEN) PERIOD V- UNTIL MARKETING APPROVAL

5.4.1 First year of LT-OLE-PEN period

5.4.1.1 PEN Visit 1 (PEN V1) – Dosing Day

Upon regulatory clearance of protocol Amendment 9 and sponsor's written approval, patients will be requested to come to the clinic for a visit named PEN Visit 1 (PEN V1). PEN V1 will occur on a planned dosing day, sites should make any effort to schedule this visit according to the current visit schedule and consider to combine visits in order to minimize the burden on the patients. Patients should arrive at the clinic prior to dosing. The visit will serve as 'baseline' to the LT-OLE-PEN period, in which the consent/assent form for the LT-OLE-PEN period will be signed. Patients should return used and unused vials that were dispensed during the study and kept at patient home. Site staff should remind the patients to bring all vials dispensed during the study (used and unused) before the visit.

OPKO Biologics	Protocol for Clinical Study CP-4-004	Page 61 of 133
Effective Date: Date of final electronic approval		

Prior to rolling over into the LT-OLE-PEN period, specific period inclusion/exclusion criteria should be assessed (as specified in section [4.1](#)). In addition changes in status of ongoing AEs or concomitant medications since completion of the LT-OLE period IV.

During PEN V1, the patients will be trained on the use of the PEN, the PEN will be dispensed, and the first PEN dose will be administered at the clinic by the parents/legal guardians. Patient will continue his/her treatment with the same dose level as before the switch to PEN. Patients will be provided with updated patient diary, instructions for use and dosing instructions.

The following will be done during PEN V1, pre dose:

- Auxology measurements (actual height measured on calibrated stadiometer);
- Body weight measurement;
- Adjustment of dose for weight;
- AEs;
- Urine pregnancy test for females of child bearing potential (In case of positive result please refer to section [7.4](#));
- Local tolerability;
- Concomitant medication;
- Dispensing of drug;
- Return of all used and unused vials;
- IGF-I, IGFBP-3 and MOD-4023 serum levels (PK);
- Anti MOD-4023 antibodies (ADA);
- Physical examination;
- Vital signs;
- Parameters of glucose metabolism (fasting glucose, fasting insulin and HbA1c);
- Routine safety laboratory (biochemistry, hematology and urinalysis);
- Other hormonal levels (TSH, free T4 and cortisol);

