5.8 DOSE MODIFICATION AND DISCONTINUATION

The following symptoms and laboratory abnormalities measured at a single occasion or repeatedly, are considered to be the main guide for the decision about dose modification or treatment interruption:

- Growth factors plasma levels:
 - **Repeated consecutive IGF-I > +2.0 SDS**
- Glucose tolerance
 - HbA1c level > 6.2 %
 - Fasting glucose level is > 5.5 mmol/L
- Increase of liver enzymes ($\geq 2x$ of ULN)
- Immune response
 - Development of high anti-growth hormone antibody titre with strong neutralizing effect
- Any other CTC grade 3 or 4 laboratory abnormality
- Development of intracranial hypertension or pseudotumor cerebri - If a patient has persistent severe headaches for more than 1 day not relieved by aspirin or other analgesics or visual disturbances, then examine the patient for papilledema (to be confirmed by an ophthalmologist). If there is papilledema, perform an MRI of the head with contrast; if there are signs of intracranial hypertension, perform a lumbar puncture (LP) and record the opening pressure. Only positive MRI findings and increased opening pressure on LP confirm the diagnosis of pseudotumor.

In the Main Study, dose efficacy will be analysed first after 6 months of treatment on an individual patient level. Patients who do not achieve the minimally satisfactory growth rate (i.e. delta height SDS of at least 0.2) at this time point will be moved to the next highest dose group for the remaining 6 months of treatment. Dose efficacy will be analysed again after 12 months of treatment on an individual patient level. Patients who do not achieve the minimally satisfactory growth rate at this time point will be moved to the next highest dose group. If the patient is in the highest dose group, the Coordinating Investigator of the study will be informed.

OPKO Biologics	Protocol for Clinical Study CP-4-004	Page 73 of 133
Effective Date: Date of final electronic approval		

Cohort 1-3 patients transitioning to the OLE will continue with the same dose (mg/kg) in which they completed the main study.

In the OLE period, the patients who were in cohort 4, in the main study (e.g. treated with Genotropin) will be randomized to one of the MOD-4023 treatment groups.

In the LT-OLE period, all patients will be switched to the highest MOD-4023 dose 0.66 mg/kg/week.

In the LT-OLE-PEN period, patients should continue with the same dose.

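### Exclusion 25 reuses the early-treatment response threshold as an entry bar to the PEN period, so a child who has caught up and holds a constant height SDS on the top dose is excluded

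*Protocol*

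**What the plan says.** **Entry to Period V.** Exclusion 25 stands among the criteria specific to the PEN period, in the synopsis and in Protocol 4.2. It defines unsatisfactory response as "improvement of height SDS of less than 0.2 SDS in a 6-month treatment interval if dose increase at this time point is not feasible". Section 5.4.1.1 puts it to use at PEN Visit 1: "Prior to rolling over into the LT-OLE-PEN period, specific period inclusion/exclusion criteria should be assessed".

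**Dose at that point.** Section 5.8 states: "In the LT-OLE period, all patients will be switched to the highest MOD-4023 dose 0.66 mg/kg/week". The dose then stays the same in Period V. There are exceptions. Section 5.3 allows a different medical decision, and 5.8.1 and 5.8.3 allow reductions to 0.56 and 0.48 mg/kg/week for adverse events or raised IGF-I.

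**Where the threshold comes from.** Section 5.8 applies 0.2 SDS first at month 6 of the Main Study and again at month 12. A child who falls short moves up one dose group. For a child with no higher group, the step is: "If the patient is in the highest dose group, the Coordinating Investigator of the study will be informed".

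**Discontinuation.** Three items of section 4.6 bear on the point:
- Item 6 (synopsis item 5) repeats the rule with a limit: "if dose increase at this time point is not feasible (Applicable for periods I-IV").
- Item 13 (synopsis item 12) gives Period V its own stop, based on growth rate over 12 months; its value is redacted.
- Item 10 (synopsis item 9) has no period limit: "Patient meets one of the exclusion criteria during the study".

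**The concern.** Early in treatment the 0.2 threshold serves to raise the dose of a child who responds poorly. At PEN entry, dose escalation is used up for nearly everyone, and the same number decides whether the child may go on at all. It asks for continued catch-up and has no end point: nothing exempts a child who has reached the normal range or the target height.

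Two things are at stake. If the criterion is followed, children growing at a normal rate lose a treatment that the synopsis offers until marketing approval, and the PEN growth tables (SAP Tables 14.2.1.2 and 14.2.3.2) describe a group chosen partly on its recent growth. If it is not followed, the same children enter as eligibility deviations.

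**Working it through.** The threshold has no stated derivation, so there is no plan figure to reproduce. The check applies the rule to simple cases and then compares the sections.

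**1. A child at constant height SDS.** Gain = 0.0, and 0.0 < 0.2. On the top dose with no increase feasible, exclusion 25 is met.

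**2. The rate that the threshold implies.** 0.2 per 6 months × 2 = 0.4 SDS per year. A child who just passed every interval would have gained:

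| Years of treatment | Cumulative gain | Height SDS from −2.0 | Height SDS from −3.0 |
|---|---|---|---|
| 2 (entry to LT-OLE) | 0.8 | −1.2 | −2.2 |
| 3 | 1.2 | −0.8 | −1.8 |
| 5 (Main Study + OLE years 1–4) | 2.0 | 0.0 | −1.0 |

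The start at −2.0 is the limit of inclusion 5a: "Height (HT) of at least 2.0 standard deviations (SD) below the mean height for chronological age (CA) and gender". Such a child would stand at the population mean after five years, and a gain of 0.1 in the next six months would still count as unsatisfactory. The table shows what the rate means. It does not claim that each child is tested at every interval.

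**3. Measurement error (assumption).** The documents give no error SD for a 6-month change in height SDS. Taking 0.03 to 0.15, P(observed gain < 0.2) = Φ((0.2 − true gain)/SD):

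| True 6-month gain | SD 0.03 | SD 0.05 | SD 0.10 | SD 0.15 |
|---|---|---|---|---|
| 0.0 | 1.00 | 1.00 | 0.98 | 0.91 |
| 0.1 | 1.00 | 0.98 | 0.84 | 0.75 |
| 0.2 | 0.50 | 0.50 | 0.50 | 0.50 |
| 0.3 | 0.00 | 0.02 | 0.16 | 0.25 |

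Across this range a child at constant SDS meets the criterion with probability at least 0.91.

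**4. The sections side by side, for a top-dose child with a gain below 0.2.**

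| Place | Consequence | Periods |
|---|---|---|
| 5.8 | Coordinating Investigator informed | written for the Main Study; 5.8 later carries its dose-modification rules forward |
| 4.6 item 6 | may be discontinued | I to IV |
| 4.2 exclusion 25 | not eligible | entry to V |
| 4.6 item 10 | may be discontinued | no limit stated |
| 4.6 item 13 | separate growth-rate stop | V |

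The rule is thus lifted as a discontinuation reason in Period V but kept as the condition for getting there. The protocol also does not say which 6-month interval counts at PEN Visit 1.

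**The case against.** The strongest reply is that the pieces fit together: exclusion 25 is a single gate at PEN Visit 1, item 6 governs treatment before it, and item 13 takes over afterwards. Most of this stands. Item 10 is permissive. If it re-applied every exclusion, exclusion 12 (methylphenidate) would clash with exclusion 24 and section 6.7.3, which except ADHD drugs in Period V. A reader might infer that the protocol contradicts itself outright on Period V. The documents do not go that far: item 10 could be read to bring exclusion 25 back, and a clarifying phrase is enough. But the gate reading leaves the main point untouched, since the child at constant SDS is stopped at the gate.

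A reader might also take section 4 as making the exclusion binding: "Patients must meet all of the inclusion and none of the exclusion criteria to be eligible". The next sentence there places eligibility checks before randomization, so it concerns Main Study entry. The force of exclusion 25 comes from its own wording and from 5.4.1.1.

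A third inference would be that the SAP hides what happened. It does not. SAP 8.1 lists and summarizes protocol deviations by period. Listings 16.2.1.2 and 16.2.1.3 (eligibility criteria, and those not met) and 16.2.6.1 (height SDS and its change at each visit) largely allow these children to be identified.

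Finally, SAP 10.2 censors discontinued children in the adult-height Kaplan-Meier curve, and one might infer that the curve is biased downward. That needs an exit share and an exit timing that the documents do not give, and a caught-up child at constant SDS may be years from adult height.

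**Conclusion.** The point holds as a flaw in one entry criterion. Exclusion 25, applied as written, bars a child who has caught up and grows parallel to the reference, and it selects the PEN growth summaries on recent growth. This follows from the text and from 0 < 0.2. It rests on the dose condition being met, which is the design default but not universal: for some children on a reduced or individually chosen dose, an increase may be feasible.

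The number of children affected cannot be computed. The documents report no yearly gains in the extension and no counts of use. For scale, 53 children started the OLE (SAP 4.1), so each is 1/53 = 1.9% of that group; how many reached PEN entry is not stated. Nor do the documents settle the size or direction of any effect on the PEN tables. The extension is descriptive, without hypothesis tests, so no formal inference is at risk. This is a low-cost change worth considering.

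**What to change.** **Protocol, synopsis and 4.2.** Delete exclusion 25. Alternatively, limit it to a child whose height SDS is still below the normal range, for example below −2.0 (the inclusion 5a limit), and replace automatic exclusion by review by the Medical Monitor and the Coordinating Investigator. The −2.0 cut-off is a suggestion for clinical judgement.

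**Protocol 4.6 item 10 (synopsis item 9).** State that exclusion 25 is not a reason for discontinuation in Period V.

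**SAP.** No change is essential. A row in Table 14.1.1.2 counting children who met exclusion 25 at PEN Visit 1, split by entered and not entered, is optional. If rollover is already complete, the study report can give these numbers from the existing listings. Exits for unsatisfactory response should not be counted as adult-height events, because some of these children are still growing.

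**Cost.** A few words in two places of the protocol. Heights are already measured every 3 months in LT-OLE and at PEN Visit 1, so no new data or visits are needed. The downside is that a few poor responders may enter PEN, where investigator judgement and the growth-rate stop in item 13 still apply. Because that threshold is redacted, the sponsor should confirm that it suffices before choosing deletion over the qualifier.
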